### 5. Statistics and data analysis

The primary analysis will be to calculate the prevalence of sickle cell retinopathy/maculopthy-related vision loss together with its 95% confidence interval (CI) to illustrate the uncertainty in the estimate. It is anticipated the prevalence will be approximately 10% based on data from Saidkasimova et al. With 554 subjects the prevalence can be estimated with a 95% confidence interval with a 5% width e.g. expected to be from 7.5% to 12.5%. The sample size (N) was chosen to satisfy this 5% width, given the confidence interval is expected to be p + 1.96\*sqrt(p\*(1-p)/n), where p=0.1. To obtain this number of evaluable subjects we estimate approximately 600 subjects will have to be enrolled, this allows for a drop-out rate of just under 10%.

A sample size of 600 will also allow accurate estimates of the stages of SCR and maculopathy occurrence to be obtained. For example, the following CIs are based on a French retrospective cohort of 942 patients:

	%	N	95%CI (23%-	width
Stage 0	30%	166	37%) (34%-	14%
Stage 1-2	40%	222	46%) (13%-	13%
Stage 3	20%	110	27%)	15%
Stage 4	5%	28	(8%-20%)	12%
Stage 5	5%	28	(8%-20%)	12%
	100%	554		

Other endpoints also include the calculation of the prevalence of each stage of SCR by age bracket and genotype. Sample size relevance in these circumstances can be illustrated by considering a hypothetical outcome. For example, under the null hypothesis there would be no association between prevalence and age, and given the hypothetical distributions of stage, and age below, it can be shown that the estimated correlation (Spearman Rank) has a greater than 3 SE difference (from zero) with 554 cases. This suggests powering is adequate for associations of this size, by the 'rule of three', for 85% power (Zbeta=1) and 5% sig level (Zalpha=1.96).

				Age Group					
				O. Guip					rate
N		3.1%	7.4%	8.2%	14.0%	16.9%	21.7%	9.7%	overall
	Stage/Age	16-25	 26-35	36-45	46-55	56-65	66+		
	5	1	5	6	6	5	2		
SCR	4	2	5	5	8	6	3		
	3	23	28	28	20	12	4		
	1-2	46	56	55	39	23	8		
	0	24	42	40	27	19	6		
	l	96	136	134	100	65	23	554	
		Spearm	an Rank -	0.14 (95%	CI:-0.23 t	o -0.06), p	o=0.001		

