# 1. Introduction

# 1.1 Proliferative sickle cell retinopathy

Sickle-cell disease (SCD) is one of the most common genetic disorders in the UK, with approximately 15000 people affected. It is a debilitating, multisystem disease, associated with episodes of acute illness, progressive organ damage and reduced life expectancy. There are 13 genetic variants of SCD, with HbSS genotype being most common (>70%) and most severe, followed by HbSC genotype. SCD affects predominantly people of African and Afro-Caribbean descent and evidence demonstrates inequalities in healthcare outcomes and access for people with SCD . An all-party parliamentary group inquiry reported low awareness of SCD and its complications among healthcare professionals and underinvestment in sickle cell research.

Proliferative sickle cell retinopathy (SCR) is the most common ophthalmic manifestation of SCD and can result in significant sight loss, although the prevalence in the U.K is not currently known. Decades old retrospective and cohort studies from other countries have estimated prevalence of SCR in SCD patients at up to 48% and associated with significant sight loss in up to 12%. Importantly, life expectancy for SCD has increased from 14 years in 1973 to >60 years in high-income countries with improvement in management and healthcare delivery. Evidence from cohort studies and large retrospective studies demonstrate increasing incidence of SCR with age. As such, we could expect the prevalence of SCR and potentially associated visual impairment, to be currently higher in the UK than previously reported.

Five stages of SCR were described by Goldberg in 1971. These are progressive with stages 1-3 being asymptomatic, stage 3 reflecting the presence of retinal neovascularisation in the far periphery known as seafan neovascularisation, vitreous haemorrhage (bleeding inside the eye) develops in stage 4 and rhegmatogenous and/or tractional retinal detachment in stage 5.

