#### Main study primary outcome

1. The prevalence of visual impairment due to SCR or maculopathy (defined as best corrected visual acuity LogMAR ≥ 0.3 in at least one eye) in a representative sample of the UK population with SCD

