### 3. Overall study design

## 3.1 Study design

This is a cross-sectional, non-interventional study. Potential participants will be introduced to the study by their haematologist, who will also provide them with the participant information sheet. Identification of potential participants in the haematology clinic is important to prevent ascertainment bias and sample a representative

sample of people with SCD. All patients with SCD are offered regular specialist follow-up by a haematologist in the UK. The national haemoglobinopathy registry record for 2021 reported 12904 people with SCD confirming that an overwhelming proportion of SCD patients are under specialist care in the UK. Informed consent will be obtained from willing participants by the ophthalmology team either in the eye department or over the telephone. Informed consent will be obtained prior to the collection of any data. Once consented, participants will have best corrected visual acuity (BCVA) with habitual correction and pinhole measured, a slit lamp examination of the anterior segment and fundus, spectral-domain optical coherence tomography (SD-OCT), optical coherence tomography-angiography (OCT-A) and ultra-widefield fundus photography performed in the eye department. Subsequently, the participant will have the NEI VFQ-25 questionnaire and the acceptability of retinal screening questionnaire administered.

In some departments, it may be more appropriate for the haematology team to share brief details about the study, including the study leaflet with potential participants. Interested participants can be sent the participant information sheet ahead of their eye clinic appointment.

The NEI VFQ-25 questionnaire can be administered over the telephone either at the time of consent or after the visit to the eye department. The acceptability of retinal screening questionnaire has to be administered after the retinal imaging has been performed.

If the NEI VFQ-25 is completed over the telephone, this must be done ±28 days of the eye clinic visit for examination and retinal images.

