#### 3.2 Participants and recruitment

Haematology teams in participating sites will inform consecutive patients with SCD ≥ 16 years about the study and refer to the ophthalmology unit for routine retinal screening. In units where patients have already been referred for screening but are awaiting appointments in the ophthalmology department can also be recruited in the ophthalmology department. In the ophthalmology department, patients with SCD who meet the study inclusion criteria will be invited by the clinical team to take part. Participating Trusts have been selected as they already offer or are willing to offer routine eye screening for SCD patients as part of standard of care and confirmed to have ultra-widefield fundus imaging and spectral domain OCT.

We have used the 2021 national haemoglobinopathy registry (NHR) report to identify centres treating patients with SCD in England. Eligible centres had to meet the following criteria:

- 1. At least 60 patients with SCD on the registry
- 2. Ultra-wide field fundus photography
- 3. Spectral domain OCT imaging
- 4. A routine screening programme for SCR in place or willing to institute one
- 5. Capacity and willingness to participate in the present study

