#### 3.3 Recruitment and Consent

600 individuals who have been diagnosed at any point with SCD will be identified from up to 16 geographically dispersed participating NHS Trusts across the UK.

Individuals identified to be eligible will be approached in clinic by their consultant haematologist or a member of their clinical team, who will explain the background, aims and nature of the project, and provide further information about the project in an accessible format (participant information sheet; PIS). Potential participants can also be identified from the ophthalmology waiting list if they have been referred as part of a routine screening programme from haematology. An invitation letter informing potential participants due to attend a sickle cell clinic can be sent out with appointment letters so that they are aware of the study before attending the clinic.

Interested participants will be invited to attend the eye clinic where they will be consented and research activities will occur. For those who do not speak English or would benefit from translation services, this will be funded by the study. Informed consent can also be obtained over the telephone. Potentially eligible participants who have previously given consent to contact for any research can be approached by the research team by telephone and if willing to consider participating, the PIS can be posted to them. There will be an opportunity to discuss the study before consent is obtained in the eye clinic or by telephone, and it will be made clear that the individual is free to withdraw from the study at any point.

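### The 5-point width of the primary interval holds only for 554 independent subjects at a prevalence of 10% or less, and, separately, the sampling frame (England in one section, the UK in others) does not match the claim of a representative UK sample

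*Protocol*

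**What the plan says.** **Precision.** Section 5 sizes the study on a normal-approximation interval for a single proportion. On the planning value it says "It is anticipated the prevalence will be approximately 10% based on data from" an earlier study, and on the result: "With 554 subjects the prevalence can be estimated with a 95% confidence interval with a 5% width". Enrolment is set at 600. Neither section 5 nor section 5.1 mentions site, and no design effect is applied. Section 5.1 promises a 95% confidence interval for the primary prevalence without naming a method.

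Section 3.3 recruits from up to 16 NHS Trusts. Section 1.1 reports sight loss of up to 12% in older studies from other countries, and says that SCR, and potentially the visual impairment that goes with it, could be expected "to be currently higher in the UK than previously reported".

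**Population.** Section 2.1 defines the primary outcome "in a representative sample of the UK population with SCD". Section 3.3 describes geographically dispersed Trusts across the UK. Section 3.2 says the 2021 registry report was used "to identify centres treating patients with SCD in England", and then requires at least 60 registry patients, ultra-widefield photography, spectral-domain OCT, a screening programme in place or willingness to start one, and capacity to take part.

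**The concern.** Two different things are at stake and should be kept apart.

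The first is width. The sample size was chosen to give exactly 5 points under one prevalence and independent sampling, so nothing is left over. A prevalence above 10% (within any plausible range), or any positive correlation within sites, makes the interval wider than stated. Patients of one Trust share catchment, genotype mix, haematology practice and access to eye care, so some correlation is plausible. If the final interval also ignored site, it would be too narrow for inference beyond the Trusts sampled.

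The second is bias and generalisability. Trusts are chosen by size, equipment and attitude to screening, and section 1.5 says only 40% of eye departments screen routinely. The sections also disagree on whether the frame is England or the UK. This concerns the population to which the primary estimate refers. More patients or a wider interval would not settle it.

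**Working it through.** **Inputs.** From section 5: p = 0.10, n = 554, multiplier 1.96, target full width 5 points. From section 3.3: up to 16 Trusts. From section 1.1: up to 12%. Assumed, because the protocol gives no values: ICC 0.005 to 0.02, 16 sites of equal size, and 15% as an upper planning prevalence.

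**1. The plan's own figure.** n = 1.96² × 0.10 × 0.90 / 0.025² = 553.2, rounded up to 554. Width = 2 × 1.96 × √(0.09/554) = 5.00 points. The stated figure is reproduced.

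**2. Higher prevalence, independent subjects.** Width = 2 × 1.96 × √(p(1 − p)/554).
- p = 0.12: 5.41 points
- p = 0.15: 5.95 points

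**3. Clustering.** Mean site size m = 554/16 = 34.6. Design effect DE = 1 + (m − 1) × ICC, and the width is multiplied by √DE. With site as the unit of variation, a t reference has 16 − 1 = 15 degrees of freedom, with multiplier 2.131 in place of 1.96 (a factor of 1.087).

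| ICC (assumed) | DE | p = 10%, normal | p = 10%, t (15 df) | p = 12%, normal | p = 15%, normal |
|---|---|---|---|---|---|
| 0.005 | 1.17 | 5.40 | 5.87 | 5.85 | 6.43 |
| 0.01 | 1.34 | 5.78 | 6.28 | 6.26 | 6.87 |
| 0.02 | 1.67 | 6.46 | 7.03 | 7.00 | 7.69 |

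With 10 sites instead of 16 (m = 55.4), the normal-reference widths at 10% are 5.63, 6.21 and 7.22 points.

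**4. Coverage if site is ignored.** Approximate coverage of a nominal 95% binomial interval is 2Φ(1.96/√DE) − 1, that is 93%, 91% and 87% for the three ICCs.

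**5. Why sample mix matters (illustration only).** The table in section 5 gives hypothetical stage 4 and 5 counts by age. These are not visual-impairment rates. Under 46: (3 + 10 + 11)/(96 + 136 + 134) = 24/366 = 6.6%. From 46: (14 + 11 + 5)/(100 + 65 + 23) = 30/188 = 16.0%. Overall: 54/554 = 9.7%. Moving 10 percentage points of the sample across age 46 changes the overall figure by 0.10 × (15.96 − 6.56) = 0.94 points, to 8.8% or 10.7%.

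**6. The population statements side by side.** Section 2.1: a representative UK sample. Section 3.3: Trusts across the UK. Section 3.2: centres identified in England and filtered on size, equipment and screening. If all sites come from the section 3.2 list, the first two statements do not hold. If sites elsewhere in the UK are open, section 3.2 is incomplete.

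**The case against.** The best defence is that the formula justifies a sample size and does not fix the analysis. Section 5.1 leaves the interval method open, and a statistical analysis plan that is not shown may allow for site. That stands: a reader might infer that the published interval will be too narrow, but the document does not establish it. What remains is that the width stated in the protocol has no allowance for site.

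The ICC is also an outside assumption. At 0.005 the loss is only 0.4 points, and the protocol has no data showing that impairment varies between sites. This stands too, and is why a range is given.

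Three stronger readings are tempting and should not be drawn.

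- *That the protocol expects a prevalence above its planning value.* Section 1.1 is hedged, is mainly about SCR, gives no figure and compares with older foreign studies in which 12% is a maximum. Section 5 explicitly anticipates about 10%. The protocol allows for a higher figure and no more.
- *That recruitment from eye-clinic waiting lists contradicts section 3.1.* Section 3.1 says "Identification of potential participants in the haematology clinic is important to prevent ascertainment bias", and section 3.3 says "Potential participants can also be identified from the ophthalmology waiting list". But section 3.3 goes on to limit that route to patients referred by haematology for routine screening, and section 3.2 has haematology teams inform consecutive patients. Some residual selection is possible; a contradiction is not shown.
- *That the sample is settled as English.* Section 3.3 says otherwise, so this is an inconsistency to reconcile.

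Finally, the age illustration rests on hypothetical counts and an arbitrary shift, and its 0.9-point effect lies inside the planned ±2.5 points.

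**Conclusion.** The point holds in two separate parts.

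**Precision.** There is no calculation error. The 5-point width is the most favourable case at 10% prevalence, with no margin. Prevalence alone takes it to 5.4 points (12%) or 6.0 (15%). Clustering alone, at 10% with 16 equal sites and an assumed ICC of 0.005 to 0.02, takes it to 5.4 to 6.5 points with a normal reference and about 5.9 to 7.0 with a t reference. The loss is modest at the low end and material at the high end. It does not make the study uninformative or call for a larger sample, since no decision in the protocol depends on exactly 5 points.

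**Population.** Sections 2.1, 3.2 and 3.3 disagree about the frame, and the site criteria are selective, so the claim of a representative UK sample is not supported as written. This rests on the text alone and needs no assumption. It affects what the estimate refers to, not the width of the interval.

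**What to change.** **Precision.**
- State that the primary 95% interval will allow for site. The exact method, such as a design-based or GEE interval with a t reference on sites minus one degrees of freedom, can go in the statistical analysis plan.
- Replace the single 5-point figure in section 5 with expected widths over a prevalence range such as 10% to 15% and stated ICCs. The multiplier should match the planned interval: with a t reference the range at 10% prevalence is about 5.9 to 7.0 points.
- Leave the sample size unchanged.

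**Population.**
- Reconcile sections 2.1, 3.2 and 3.3, or limit the claim to the kind of centre actually sampled.
- Report a prevalence standardised to the national registry's age and genotype distribution beside the crude value, if that tabulation can be obtained. The protocol shows only a registry total and its use in finding centres. Year of birth and genotype are already collected (section 3.1).
- Optionally, record recruitment route and report the estimate with and without waiting-list recruits.

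**Cost.** Changes of wording, a registry tabulation and, if the option is taken, one eCRF field. The price is a wider, less favourable stated interval and possibly a narrower population claim.

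### In the stage-precision table, three of the five confidence intervals use the stage's own count as denominator instead of 554, and the stage 4 and 5 intervals exclude their own 5% estimate

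*Protocol*

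**What the plan says.** Section 5 of the protocol (Statistics and data analysis) derives the sample size from the primary outcome, visual impairment due to SCR or maculopathy, with an expected prevalence of 10%: "With 554 subjects the prevalence can be estimated with a 95% confidence interval with a 5% width". The formula is given there: "The sample size (N) was chosen to satisfy this 5% width, given the confidence interval is expected to be" p ± 1.96·sqrt(p(1−p)/n). Enrolment is then set at 600 to allow for drop-out.

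The section goes on to secondary precision: "A sample size of 600 will also allow accurate estimates of the stages of SCR and maculopathy occurrence to be obtained". By way of example, "the following CIs are based on a French retrospective cohort of 942 patients", and a table follows. Its rows are:

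| Stage | % | N | 95% CI | Width |
|---|---|---|---|---|
| 0 | 30% | 166 | 23-37% | 14% |
| 1-2 | 40% | 222 | 34-46% | 13% |
| 3 | 20% | 110 | 13-27% | 15% |
| 4 | 5% | 28 | 8-20% | 12% |
| 5 | 5% | 28 | 8-20% | 12% |
| Total | 100% | 554 | | |

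In the text copy of the protocol the lower limits of the first three rows sit one line too high. That is a layout effect and is not counted as an error. The stage 4 and 5 rows are intact.

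The prevalence of each SCR stage belongs to the first secondary objective (section 2) and is the first secondary outcome (section 2.1). Section 5.1 takes one eye per participant, the one with the worse stage, so each participant contributes one stage.

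**The concern.** The prevalence of a stage is the number of participants in that stage divided by all participants with a stage, here 554. The precision of that proportion depends on the 554, not on how many fall in the stage. The printed widths of 12 to 15 percentage points are far larger than a sample of 554 gives. Section 5 itself obtains a width of 5 points from the same 554 at a prevalence of 10%, so a width of 12 points at a prevalence of 5% cannot come from the same calculation. In the stage 4 and 5 rows the estimate lies below the lower limit of its own interval.

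At stake are the only precision figures the protocol gives for overall stage prevalence. Someone using the table for stages 4 and 5 would expect about ±6 points around an unexplained 14%, when the design gives about ±1.8 points around 5%.

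**Working it through.** **Inputs, all from section 5.** Evaluable n = 554. Interval p ± 1.96·sqrt(p(1−p)/n). Stage percentages 30, 40, 20, 5, 5. Stage counts 166, 222, 110, 28, 28.

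**Step 1: the primary figure reproduces.** For a half-width of 0.025 at p = 0.10, n = 1.96² × 0.10 × 0.90 / 0.025² = 553.2, rounded up to 554. The interval is 7.5% to 12.5%, as printed.

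**Step 2: what the N column is.** 166 + 222 + 110 + 28 + 28 = 554, and for example 166/554 = 30.0% and 28/554 = 5.1%. Each N is therefore the expected count in the stage, the numerator.

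**Step 3: the printed intervals with the stage count used as n.**

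| Stage | p | n used | Computed CI | Computed width | Printed | Match |
|---|---|---|---|---|---|---|
| 0 | 0.30 | 166 | 23.0-37.0% | 13.9 | 23-37%, 14 | yes |
| 1-2 | 0.40 | 222 | 33.6-46.4% | 12.9 | 34-46%, 13 | yes |
| 3 | 0.20 | 110 | 12.5-27.5% | 15.0 | 13-27%, 15 | yes |
| 4, 5 | 0.05 | 28 | −3.1 to 13.1% | 16.1 | 8-20%, 12 | no |

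In the first three rows limits and widths agree to rounding. For stage 1-2 and stage 3 the printed width is one point more than the difference of the rounded limits (46 − 34 = 12 and 27 − 13 = 14). That is what unrounded widths of 12.89 and 14.95 produce, which confirms the source of the figures.

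**Step 4: can 8-20% be traced?** At p = 0.05 the same formula gives 3.2-6.8% with n = 554, 3.3-6.7% with n = 600, and 3.6-6.4% with n = 942. At n = 28, with 1 or 1.4 events, the Wilson, exact, Agresti-Coull and Jeffreys lower limits are all at or below 1.1%. At n = 554 the same four methods give upper limits of at most 7.2%, below the printed lower limit of 8%. An interval of 8-20% is centred on 14% and would need n = 1.96² × 0.14 × 0.86 / 0.06² ≈ 128, a number found nowhere in the table.

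The 5% is not the misprint. The column reaches 100% only with 5% + 5%, and 28/554 = 5.1%. The age-by-stage illustration in the same section has 29 participants at stage 4 (29/554 = 5.2%) and 25 at stage 5 (25/554 = 4.5%).

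**Step 5: the table with n = 554.**

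| Stage | 1.96·sqrt(p(1−p)/554) | 95% CI | Width | Printed width |
|---|---|---|---|---|
| 0 | 3.8 points | 26.2-33.8% | 7.6 | 14 |
| 1-2 | 4.1 points | 35.9-44.1% | 8.2 | 13 |
| 3 | 3.3 points | 16.7-23.3% | 6.7 | 15 |
| 4 | 1.8 points | 3.2-6.8% | 3.6 | 12 |
| 5 | 1.8 points | 3.2-6.8% | 3.6 | 12 |

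For the first three rows the excess width is sqrt(554/166) = 1.8, sqrt(554/222) = 1.6 and sqrt(554/110) = 2.2. For stages 4 and 5, Wilson limits with 28/554 are 3.5-7.2% (width 3.7).

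**The case against.** The strongest defence is that nothing in the study depends on this table. It is introduced as an example. The 554 and the 600 come from the primary outcome alone, and that calculation reproduces. Every corrected interval is narrower than the printed one, so the claim of accurate stage estimates becomes stronger. All of this stands and limits the weight of the point. It does not make the printed intervals right.

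Four stronger readings are tempting, and the document does not support them:

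- That all five intervals use the stage's own count. Only three do. With n = 28 the stage 4 and 5 limits would be −3.1% and 13.1%, so their origin is unknown.
- That the sample size is wrong or too small for the stage estimates. The correction points the other way.
- That the error will carry into the final analysis. Section 5.1 does not prescribe this calculation, and section 5 uses the full 554 for the primary interval.
- That the fault is graver because stages 4 and 5 matter most for screening. The protocol's own rationale stresses early detection, calls stages 1 to 3 asymptomatic (section 1.1) and places the best-evidenced treatment at stage 3 (section 1.3).

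It is also fair to say that Wilson limits for the 5% rows are a preference. At n = 554 they differ from the protocol's formula by at most 0.4 of a point.

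**Conclusion.** The point holds as a correction of stated figures. Three of the five intervals rest on the wrong denominator and are 1.6 to 2.2 times too wide. The other two exclude the estimate they belong to and cannot be derived from any denominator in the document. The design, the enrolment target and the conclusion that stage precision is adequate are unaffected.

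The corrected limits assume that all 554 evaluable participants have a gradable stage and that the stage percentages in the table are the intended planning values. If fewer participants can be staged, the intervals widen in proportion to 1/sqrt(n). The finding that the wrong denominator was used in the first three rows, and that 8-20% cannot belong to 5%, does not depend on either assumption.

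**What to change.** Recompute the table in section 5 with n = 554:

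- stage 0: 26.2-33.8% (width 7.6)
- stage 1-2: 35.9-44.1% (width 8.2)
- stage 3: 16.7-23.3% (width 6.7)
- stages 4 and 5: 3.2-6.8% each (width 3.6) by the protocol's formula. Wilson limits of 3.5-7.2% are an acceptable alternative if the method is named.

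Label the N column as the expected number in the stage. Add one sentence saying that overall stage prevalence uses all evaluable participants as denominator, while prevalence by age bracket or genotype uses the total of that subgroup. The second half is needed because a blanket rule of 554 would be wrong for the breakdowns: the illustrative 16-25 age group, for example, has 96 participants.

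The cost is a change of wording in one table and one added sentence. Recruitment, endpoints and analysis stay as they are.
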